7.8 Compliance

Patients will be asked about investigational product administration by telephone on Day 4 and at the site on Day 7, and also on Day(s) 11 (telephone) and 14 (site) if receiving prolonged treatment. No other measurements of treatment compliance will be made. These compliance data will be summarised for the full analysis set. The rate of compliance is defined as the actual amount of study treatment taken divided by the expected amount of study treatment to be taken. The expected amount is based on the planned duration of treatment (*i.e.* for prematurely withdrawn patients, the expected amount is computed as if the patient had not withdrawn). The expected amount is 4 doses for patients without prolonged treatment and 8 doses for patients with prolonged treatment.

7.9 Primary and secondary endpoints analyses

All analyses of clinical performance endpoints will be performed on the full analysis set, and these analyses will be considered as the main analyses. If a relevant number of patients are excluded from the PP population, the per-protocol analysis set will be used for supportive clinical performance sensitivity analysis of the primary clinical performance endpoint.

If the stated assumptions that the statistical evaluation is built upon can be questioned, suitable alternative methods may be applied. For example, a 95% confidence interval based on a non-parametric method may be applied if assumption of data belonging to the normal distribution seems not to hold.

All study endpoints (primary, secondary, and exploratory), as well as the related variables specified in the list below in Section 7.9.2, will be presented descriptively.

7.9.1 Primary endpoints

- Clinical performance endpoint: Clinical cure rate on Day 7 will be calculated and presented together with a one-sided 95 % confidence interval based on the exact binomial distribution (Clopper-Pearson).
- Clinical safety endpoint: Safety and tolerability will be assessed according to Section 7.10.2.

The primary clinical performance endpoint is the Clinical cure rate on Day 7, where clinical cure is defined as the absence of all of the Amsel criteria stated in [Section 3.1.1](#) above. The primary performance objective of the trial is to show that the Clinical cure rate is above 40 %, *i.e.* to show that the lower limit of the one-sided 95 % CI for the observed cure rate is above 40 %.

Hypotheses for the primary clinical performance endpoint

Null hypothesis: Clinical cure rate is less than or equal to 40 %.

Alternative hypothesis (one-sided): Clinical cure rate is above 40 %.

The primary clinical safety endpoint, i.e. safety and tolerability based on reported treatment-emergent AEs, will be analysed descriptively only, see Section 7.10.2 below, and will thus not be connected to any formal hypothesis testing.

7.9.2 *Secondary clinical performance endpoints*

The secondary clinical performance endpoints are either binary or continuous.

The usability data, as measured by the patient questionnaire and which contain both binary and continuous endpoints, will only be presented descriptively.

The other binary secondary clinical performance endpoints will be calculated and presented together with a two-sided 95 % confidence interval based on the exact binomial distribution (Clopper-Pearson). No hypothesis testing will be made on the binary endpoints.

The only remaining clinical performance endpoint that is considered as a continuous endpoint is the change in the sum of the 3 BV symptoms scores. Here, applying Student's t distribution, a two-sided 95% confidence intervals for the arithmetic mean will be presented.

Hypothesis for the continuous secondary clinical performance endpoint "Change in the sum of the 3 BV symptoms scores"

Null hypothesis: Change from baseline is = 0.

Alternative hypothesis (two-sided): Change from baseline \neq 0.

Below follows a list of all secondary endpoints followed by information on which are binary and which are continuous. Note that, as described in [Section 3.2.1](#) above, the analyses of the secondary endpoints will be performed on 3 different patient categories. These are denoted as A, B, and C below.

A. All patients

- i] Proportion of patients being negative for each of the 3 Amsel criterion on Day 7 compared to Day 0
- ii] Proportion of patients having a reduction in the sum of the 3 BV symptoms scores (fishy smell, burning, and irritation) on Day 4 and Day 7, compared to Day 0
- iii] Change in the sum of the 3 BV symptoms scores (fishy smell, burning, and irritation) from Day 0 to Day 4 and Day 7
- iv] Proportion of patients receiving prolonged treatment
- v] Usability, measured by patient questionnaire

The endpoints i], ii], iv], and the first 4 questions in endpoint v] are binary variables.

The endpoints iii], and the 5th question in v] are considered as continuous variables.

B. For patients not receiving prolonged treatment

- vi] Recurrence rate on Day 14 and Day 35, defined as the proportion of patients clinically cured on Day 7 and thereafter responding "yes" to a yes/no question from the patient questionnaire on whether the symptoms have recurred

The endpoint vi] constitute binary variables.

C. For patients receiving prolonged treatment

- vii] Clinical cure rate on Day 14, defined as the absence of all of the 3 Amsel criteria as defined above
- viii] Proportion of patients being negative for each of the 3 Amsel criterion on Day 14 compared to Day 0
- ix] Proportion of patients having a reduction in the sum of the 3 BV symptoms scores (fishy smell, burning, and irritation) on Day 11, Day 14, Day 21, and Day 42, compared to Day 0
- x] Change in the sum of the 3 BV symptoms scores (fishy smell, burning, and irritation) from Day 0 to Day 11, Day 14, Day 21, and Day 42
- xi] Recurrence rate on Day 21, and Day 42, defined as the proportion of patients clinically cured on Day 14 and thereafter responding “yes” to a yes/no question from the patient questionnaire on whether the symptoms have recurred
- xii] Proportion of patients receiving rescue treatment on Day 14

The endpoints vii], viii], ix], xi], and xii] are binary variables.

The endpoints x] are considered as continuous variables.

In connection to the endpoints described above, the underlying variables listed below not constituting endpoints (denoted as “other related variables” in the CIP), will be presented descriptively, see DDP.

- BV symptoms: fishy smell (can take integer values in the interval 0-3)
- BV symptoms: burning (can take integer values in the interval 0-3)
- BV symptoms: irritation (can take integer values in the interval 0-3)
- Sum of all BV symptoms score (can take integer values in the interval 0-9)

7.9.3 *Exploratory endpoints*

The exploratory endpoints, see also Section 7.2 in the CIP, are listed below.

All patients

- xiii] Effect on vaginal microbiome on Day 0 and Day 7
- xiv] Vaginal pH on Day 7

For patients not receiving prolonged treatment

- xv] Effect on vaginal microbiome on Day 35

For patients receiving prolonged treatment

- xvi] Effect on vaginal microbiome on Day 14 and Day 42

The endpoints related to vaginal microbiome (endpoints xiii], xv], and xvi]) will be presented after study completion.

Vaginal pH, i.e. endpoint xiv] is considered as a continuous variable and will be presented descriptively.

7.10 *Safety evaluation*

All evaluations of safety data will be performed on the full analysis set.

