3.4 Schedule of Assessments and Procedures

Table 2 Schedule of Assessments and Procedures, No Prolonged Treatment

Evaluations	Day 0	Day 2	Day 4 (+2 days)	Day 6	Day 7 (+2 days)	Day 14 (±2 days)	Day 35 (±2 days)
	Screening		Follow-up		Follow-up	Follow-up	Follow-up
	Visit 1		Visit 2		Visit 3	Visit 4	Visit 5
	Visit		Telephone		Visit	Telephone	Telephone
Informed Consent	X						
Eligibility Criteria	X						
Pregnancy Test (Urinary)	X						
Medical History	X						
Concomitant Medications	X		X		X	X	X
Gynecological Examination Including Amsel's Criteria*	X				X		
Bacterial Vaginosis Scoring Scale	X		X		X	X	X
Recurrence						X	X
Vaginal Swab for Culture	X						
Vaginal Swab for Sequencing [#]	X				X		X
Treatment	X	X	X	X			
Vaginal pH	X				X		
Usability					X		
Adverse Events	X		X		X	X	X
Product Accountability					X		

*Includes microscopy assessment [#]Self-swab at Day 35

Table 3 Schedule of Assessments and Procedures, Prolonged Treatment

Evaluations	Day 0	Day 2	Day 4 (+2 days)	Day 6	Day 7 (+2 days)	Day 9	Day 11 (+2 days)	Day 13	Day 14 (+2 days)	Day 21 (±2 days)	Day 42 (±2 days)
	Screening		Follow-up		Follow-up		Follow-up		Follow-up	Follow-up	Follow-up
	Visit 1		Visit 2		Visit 3		Visit 4		Visit 5	Visit 6	Visit 7
	Visit		Telephone		Visit		Telephone		Visit	Telephone	Telephone
Informed Consent	X										
Eligibility Criteria	X										
Pregnancy Test (Urinary)	X										
Medical History	X										
Concomitant Medications	X		X		X		X		X	X	X
Gynecological Examination Including Amsel's Criteria*	X				X				X		
Bacterial Vaginosis Scoring Scale	X		X		X		X		X	X	X
Recurrence										X	X
Vaginal Swab for Culture	X										
Vaginal Swab for Sequencing [#]	X				X				X		X
Treatment	X	X	X	X	X	X	X	X			
Vaginal pH	X				X						
Usability					X				X		
Adverse Events	X		X		X		X		X	X	X
Product Accountability					X				X		

*Includes microscopy assessment [#]Self-swab at Day 42

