3.5.10 Day 14 (+2 Days); Follow-up Visit

Applicable to patients receiving prolonged treatment

Patients receiving prolonged treatment at Day 7 due to still-present BV symptoms will visit the site on Day 14 to have gynecological examination performed and 3 Amsel criteria assessed by the Investigator or an authorized designee. Patients will receive an antibiotic according to clinical routines should symptoms still be present.

Vaginal samples will be collected by swab to be used for sequencing analysis of the vaginal microbiome.

In addition, patients will be asked questions from the patient questionnaire to assess: symptoms of BV (fishy smell, irritation, and burning); usability; and AEs, if any.

Procedures performed:

- Gynecological examination by Investigator or an authorized designee assessing the presence of BV according to the following Amsel criteria:
 - Presence of thin, white, homogenous discharge
 - Presence of clue cells on microscopy (more than 20% of epithelial cells)
 - Release of fishy odor “i.e. a positive whiff test“ when alkali (10% potassium hydroxide [KOH] solution) is added
- Symptoms of BV (fishy smell, irritation, and burning) evaluated by patients according to a scoring scale (0-3)
- Vaginal swab for sequencing
- Recording of:
 - concomitant medications,
 - adverse events, and
 - usability

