3.5.11 Day 21 (± 2 Days); Follow-up Telephone Contact

Applicable to patients receiving prolonged treatment

Patients receiving prolonged treatment on Day 7 will be contacted by the Clinical Trial Unit by telephone on Day 21. Patients will be asked questions from the patient questionnaire pertaining to BV symptoms (fishy smell, irritation, and burning). Questions on concomitant medications, recurrence, and AEs, if any, will also be asked.

Procedures performed:

- Bacterial vaginosis recurrence
- Symptoms of BV (fishy smell, irritation, and burning) evaluated by patients according to a scoring scale (0-3)
- Recording of:
 - concomitant medications, and
 - adverse events

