3.5.13 Day 42 (± 2 Days); Follow-up Telephone Contact

Applicable to patients receiving prolonged treatment

Patients receiving prolonged treatment will be contacted over telephone by the Clinical Trial Unit on Day 42 and asked questions from the patient questionnaire relating to BV symptoms (fishy smell, irritation, and burning). Patients will also be asked questions on recurrence, concomitant medications, and AEs, if any. Patients will collect vaginal samples by self-swab to be sent by post to laboratory for sequencing.

Procedures performed:

- Bacterial vaginosis recurrence
- Symptoms of BV (fishy smell, irritation, and burning) evaluated by patients according to a scoring scale (0-3)
- Vaginal swab for sequencing
- Recording of:
 - concomitant medications, and
 - adverse events

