This is an open-label, single-armed, multi-center study to evaluate clinical performance, tolerability, and safety of Gedeo Pessary in 24 adult women with BV. Patients seeking treatment can be screened for study participation. Included patients will have gynecological examination, including collection of vaginal samples, and will receive the investigational product to be self-administered at Day(s) 0, 2, 4, and 6. Patients will again be examined after 7 days. Prolonged treatment at Day(s) 7, 9, 11, and 13 will

be given to patients not cured at Day 7; including re-examination at Day 14. Patients will be followed up by telephone up to 29 days after last treatment administration. Gynecological examinations include collection of Amsel criteria. Vaginal samples will be used for confirming diagnosis and microbiome analyzes. Patient questionnaires will be used for assessing BV symptoms, usability, and AEs.

Figure 1 Study Flow Chart

AC = Amsel's Criteria, BVS = Bacterial Vaginosis Symptoms, VS = Vaginal Swab (*Self-swab at home)

Patients not receiving prolonged treatment applies to patients cured at Day 7. If not cured, the flow chart *patients receiving prolonged treatment* applies. Patients will here receive an antibiotic if not cured at Day 14. Adverse events will be assessed throughout the study.

5 Study population

This study will include patients with BV. Twenty-four (24) patients are planned to be treated under this CIP

Post-menarchal, pre-menopausal females aged 18 years or older seeking treatment for symptoms of BV at study sites' gynecological clinics may be informed about the study and asked about their willingness to participate.

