The decision on the classification of patients to each analysis set will be taken at the clean file meeting and documented in the clean file report together with the reasons for excluding patients from analysis sets.

7.2.1 *Full analysis set*

Full Analysis Set (FAS): This is the primary population and comprises all patients entering the study and having received at least 1 dose of study treatment. Analyses of clinical performance will be performed against this population.

In addition to this, two sub-populations based on this FAS will be formed: “FAS (For patients not receiving prolonged treatment)”, and “FAS (For patients receiving prolonged treatment)”.

7.2.2 *Per-protocol analysis set*

Per Protocol (PP) Population - This will include all FAS patients without any major protocol deviation, i.e. patients who have completed the study and sufficiently complied with the study protocol, have available primary endpoint data and have received the study treatment according to protocol. The final definition of a major protocol deviation will be decided and defined at the clean file meeting and

documented in the clean file report. If a relevant number of patients are excluded from the PP population, then the analysis of the clinical performance endpoint will be provided for the PP population.

7.2.3 *Safety analysis set*

The safety analysis set will be based on the same definition as used for FAS. All safety analyses will therefore be performed against the FAS. All patients included in the FAS will be accounted for, including those who did not complete the study along with the reasons for withdrawal.

7.3 *Disposition of patients*

The following will be presented:

- Number of screened patients, in total.
- Number of screening failures, in total.
- Number of enrolled patients.

Based on the number of enrolled patients, the following will also be presented:

- Number and percentage of patients who did not receive any dose of study treatment.
- Number and percentage of patients who received at least one dose of study treatment.
- Number and percentage of patients who completed the study.
- Number and percentage of patients who withdrew prematurely from the study.
- Number and percentage of patients in each of the analysis sets.

In addition, a frequency table on the primary reason for premature withdrawal from the study will be presented. Percentages for this table will be based on the number of prematurely withdrawn patients.

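### At Day 21 and Day 42, endpoints ix and x have no rule for symptom scores taken after the Day 14 rescue antibiotic, so antibiotic response can be counted as pessary performance

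*SAP*

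**What the plan says.** **Rescue.** The study flow text in SAP 4 says of the prolonged-treatment group: "Patients will here receive an antibiotic if not cured at Day 14". Protocol 3.5.10 words the trigger by symptoms: "Patients will receive an antibiotic according to clinical routines should symptoms still be present". Protocol 5.2.1 leaves the prescription to what is considered necessary.

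**Scoring after rescue.** In protocol Table 3 the row "Bacterial Vaginosis Scoring Scale" is marked at Day 21 and Day 42. The visit sections agree: "Patients receiving prolonged treatment on Day 7 will be contacted by the Clinical Trial Unit by telephone on Day 21" (3.5.11) and "Patients receiving prolonged treatment will be contacted over telephone by the Clinical Trial Unit on Day 42" (3.5.13). Both list symptom scoring, and neither excepts rescued patients.

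**Analysis.** SAP 7.2.1 forms the sub-population "FAS (For patients receiving prolonged treatment)". SAP 7.9.2 lists ix and x for this group as secondary clinical performance endpoints; the days for x read "burning, and irritation) from Day 0 to Day 11, Day 14, Day 21, and Day 42". SAP 8.7 counts any change below zero as a reduction. SAP 7.1.5 uses observed data without imputation. For x, SAP 7.9.2 sets a two-sided test: "Null hypothesis: Change from baseline is = 0".

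**Where rescue appears.** Rescue is reported as its own endpoint (xii), and SAP 8.10 puts its start and stop dates in listings. The per-protocol sensitivity analysis in SAP 7.9 covers only the primary performance endpoint.

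**A possible exception.** Protocol 3.6 says that patients given an antibiotic on Day 14 are followed up for safety assessments. It does not say whether symptom scoring stops.

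**The concern.** The antibiotic is given for the condition whose symptoms ix and x measure, and it is given to the patients in whom the pessary has not produced cure. A score taken one or four weeks later reflects the pessary followed by an antibiotic. The SAP nevertheless presents that score under clinical performance, pooled with scores from patients who had the pessary alone.

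With no control arm, a reader has nothing to set the late symptom figures against and will take them as product performance. The neighbouring recurrence endpoint xi does not have this problem, because SAP 7.9.2 restricts it to patients cured on Day 14. Endpoints ix and x carry no such restriction.

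**Working it through.** The documents give no expected value for ix or x and no expected rescue rate, so there is no planned figure to reproduce. The check traces one rescued patient through the rules and then sizes the effect.

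**1. Trace.** A patient not cured on Day 7 joins the prolonged sub-population. Not cured on Day 14, she receives an antibiotic. Table 3 has her scored on Days 21 and 42. Those scores are observed, so SAP 7.1.5 uses them. If the sum is below Day 0, SAP 8.7 counts a reduction in ix, and the change enters the mean and test of x. No step refers to the antibiotic. Day 11 precedes rescue, and the Day 14 score is taken at the visit where rescue is prescribed, so neither is affected.

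**2. Size of the group.** At the planned 70 % cure rate: 24 × (1 − 0.70) = 7.2 patients (binomial 5th to 95th percentile 4 to 11). At 40 % cure: 24 × 0.60 = 14.4.

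**3. Effect on ix.** Let m be the number of prolonged patients and k the number who improve only after the antibiotic. The inflation is k/m.
- m = 7: k = 0 gives 0; k = 1 gives 1/7 = 14.3 points; k = 2 gives 28.6 points.
- Per patient: 1/4 = 25 points at m = 4; 1/11 = 9.1 at m = 11; 1/14 = 7.1 at m = 14.

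The value of k is unknown. If Day 14 cure were also 70 % (assumption), about 24 × 0.3 × 0.3 = 2.2 patients would be rescued. In shares, inflation = q(1 − e)r, where q is the share rescued, e the share of those already improved, and r the share of the rest who improve on the antibiotic. As an assumed range, r runs from 0.70 × 0.70 = 0.49 (70 % cure from protocol 1.1, 30 % relapse at 4 weeks from the clindamycin cream row of Table 1) to 0.80 (no relapse).

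| q | e = 1 | e = 0.5 | e = 0 |
|---|---|---|---|
| 0.3 | 0 | 7 to 12 points | 15 to 24 points |
| 0.5 | 0 | 12 to 20 points | 25 to 40 points |

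This assumes that rescued patients would otherwise have stayed as they were, and that a cure rate can stand in for any symptom reduction.

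**4. Effect on x.** Shift = share rescued × their mean change after the antibiotic. With half rescued, each 1-point fall moves the mean by −0.5. Unlike ix, x shifts even if every rescued patient had already improved.

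**5. Illustration with invented scores**, to show the mechanism only. Seven patients, four rescued. Changes from Day 0: non-rescued −4, −3, −2; rescued before the antibiotic 0, 0, −1, +1; rescued after it −3, −3, −4, +1.

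| Handling | ix (exact 95 % CI) | Mean x (95 % CI), p |
|---|---|---|
| As written | 6/7 = 85.7 % (42.1 to 99.6) | −2.6 (−4.2 to −1.0), 0.007 |
| Rescued at pre-rescue values | 4/7 = 57.1 % (18.4 to 90.1) | −1.3 (−2.9 to 0.4), 0.11 |
| Rescue counted as no reduction | 3/7 = 42.9 % (9.9 to 81.6) | not applicable |
| Non-rescued only | not applicable | −3.0 (−5.5 to −0.5), 0.035 |

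Check on x: sums −18/7 = −2.571 and −9/7 = −1.286; the shift is 4/7 × (−2.25) = −1.286. The intervals overlap widely.

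**6. If protocol 3.6 means safety follow-up only.** Rescued patients then have no score. SAP 7.1.1 keeps patients with missing data in the denominator, so ix would be 3/7 in the illustration and is largely protected. The mean of x would rest on the non-rescued alone, a group selected for Day 14 cure.

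**The case against.** **Protocol 3.6 may remove the problem.** Read as safety-only follow-up, it leaves no post-antibiotic symptom scores. This is a fair reading of one sentence, but the visit schedule points the other way, and under it x is still restricted to a selected group. A reader might infer that x is then certainly biased towards the pessary. The documents do not support that: SAP 4 ties rescue to Amsel cure, not to the symptom sum, so a rescued patient may have improved as much in symptoms as a non-rescued one. The bias is probable, not certain.

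**The size is assumption-driven.** This stands. The 40-point corner of the table or the change in p-value in the illustration might be taken as a forecast; neither is. The 30 % relapse figure fits Day 42 better than Day 21. Later improvement could also come from delayed pessary effect or spontaneous change: the last dose is on Day 13 with release over 45 hours.

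**Much is already disclosed.** Day 14 cure, Day 14 symptoms and the rescue proportion are reported for the same group, and rescue dates are listed. With about 7 patients a careful reader could trace the overlap by hand. A reader might go further the other way and infer that the planned tables fail to separate rescued patients. That cannot be said, because the mock tables are in the Data Display Plan, which is not among the documents. Only the SAP text is silent.

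**Using observed scores regardless of rescue is a recognised strategy.** So it is, but it estimates the pessary followed by an antibiotic where needed. A single-arm test of that against zero is not a test of the pessary, and the SAP does not label it so.

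**Conclusion.** The point holds as a gap in the rules for two secondary endpoints at two late time points. As written, SAP 7.9.2 and 8.7 allow antibiotic response to count as pessary performance in ix and x at Days 21 and 42, and to enter the test of x. Under the safety-only reading of protocol 3.6, ix is largely protected and x rests on a selected group.

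The size cannot be fixed in advance. For ix it is zero if rescued patients had already improved, and about 14 points for each patient who improves only after the antibiotic, assuming 7 prolonged patients.

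A reader might infer that the trial's performance conclusion is compromised. It is not: the 40 % hypothesis concerns Day 7 only, and the Day 7 endpoint, the Day 11 and 14 results and recurrence endpoint xi are untouched. In a 24-patient feasibility study this is of low to moderate severity, worth correcting because the correction is cheap.

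**What to change.** In SAP 7.9.2 and 8.7, for Day 21 and Day 42 only:

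1. State whether rescued patients are scored for symptoms, which settles the reading of protocol 3.6.
2. Keep the all-observed ix and x, labelled as including scores taken after a rescue antibiotic.
3. Show both by rescue status, defined by whether the rescue start date precedes the assessment, with a note that the non-rescued group is selected for Day 14 cure.
4. Add a supportive row for ix in which rescue counts as no reduction and the full denominator is kept.
5. State that the all-patient test of x at these days is not interpreted as a pessary effect.

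The cost is SAP wording and one table split, using scores and dates already collected. The split groups will be very small (3 and 4 patients in the illustration), the late figures will look less favourable, and the supportive ix row is conservative for anyone who had improved before rescue. Showing it beside the observed result avoids imposing one strategy.
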